#### **Interim Analysis**

An interim analysis for the primary efficacy evaluation was planned to be conducted after all subjects have completed at least 6 months in the study or had been withdrawn. For this Phase 2 trial, efficacy and safety evaluation beyond Month 6 will be considered exploratory.

Safety monitoring committee (SMC) reviews will be performed throughout the study. The unmasked SMC reviewed unmasked listings for 31 subjects on 29 March 2018 (data cutoff 09 March 2018), and requested that recruitment be temporarily paused pending further data analysis. Additional descriptive efficacy summaries were provided to the SMC for a review meeting on 25 April 2018. An unmasked team from the sponsor presented further data for an unmasked SMC meeting held on 18 August 2018 (data cutoff 06 August 2018). Following this meeting, the SMC approved the sponsor's proposal to enroll additional subjects treated with the Group 3 dose and a new Group 4 dose (containing a greater volume of the same formulation of Group 3). As of Protocol Amendment 3 (v4), data from Part 1 (31 subjects) will be unmasked. Given that, as of protocol preparation, 1) all 31 subjects randomized in Part 1 have completed at least Month 7.5 in the trial or have been withdrawn (and evaluations beyond 6 months were considered exploratory); 2) no formal statistical comparisons will be made between the groups in Part 1 or Part 2; and 3) the selection of dose to carry forward from Part 1 has already been decided, it was deemed that minimal bias will be introduced by unmasking the data. The sponsor intends to disclose key unmasked efficacy and safety data from Part 1 with the investigators and other stakeholders so that they can adequately understand the benefits and risks of the study treatment.

For Part 2, no formal interim analysis is planned.

## Summary of Known and Potential Risks and Benefits to Human Subjects

ProDex is developed to provide an ideal, safe, long-acting, DSP delivery system for the treatment of macular edema.

Subjects receiving ProDex IVT injection may be at risk for transient vitreous opacity, which might result in transient visual acuity decrease but would be expected to resolve within 2-6 weeks after study drug dosing. IVT injections have been associated with endophthalmitis, eye inflammation, increased IOP, vitreous hemorrhage, and retinal detachments. Subjects should be monitored following the injection. Use of corticosteroids may produce posterior subcapsular cataracts, increased IOP, glaucoma, and may enhance the establishment of secondary ocular infections due to bacteria, fungi, or viruses.

From the experience of preclinical and preliminary clinical data, the expected adverse reactions of ProDex IVT injection on subject with macular edema following CRVO and BRVO include vitreous opacity, increased IOP, visual acuity decrease, conjunctival hemorrhage, eye pain, dry eye, foreign body sensation, conjunctival hyperemia, cataract, floaters, and hypertension. Previous human experience from Ozurdex shows that potential adverse reactions include vitreous detachment, optic nerve damage, visual acuity and field defects, posterior subscapular cataract formation, secondary ocular infection, and perforation of the globe where there is thinning of the cornea or sclera. The expected systemic adverse reactions such as hypertension, hyperglycemia, vasovagal reaction, and facial flushing are also rare, but will be monitored carefully.

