# Secondary:

- Change from baseline of retinal CST (using SD-OCT) in the study eye at scheduled visits
- Proportion of subjects with retinal CST (using SD-OCT) <300 µm in the study eye at scheduled visits
- Change from baseline in number of letters read correctly (using BCVA) in the study eye at scheduled visits
- Proportion of subjects with BCVA gain of 15 or more letters from baseline in the study eye at scheduled visits
- Proportion of subjects with BCVA letter score >73 (20/40 Snellen equivalent) in the study eye at scheduled visits
- Time to achieve a treatment response of gain of 15 or more letters from baseline BCVA in the study eye
- Adverse Events (AEs)
- IOP
- Slit lamp biomicroscopy (SLB)
- Indirect ophthalmoscopy (dilated)
- Fundus photography (FP)
- FA
- Physical examination
- Vital signs (BP, pulse)
- Clinical laboratory evaluations (routine hematology, chemistry, and urinalysis)

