# Safety Measures:

TLC399 (ProDex)	Taiwan Liposome Company, Ltd.
Clinical Trial Protocol: TLC399A2002	12 October 2018, v5.0

observations, mean, standard deviation, median, minimum, and maximum, as well as number of missing data (if relevant); while categorical variables will be presented as number of observations, count, percentage, and number of missing data (if relevant) in a frequency table. In general, missing values will remain as missing. Specific rules for handling missing efficacy data are described in Efficacy Analysis.

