### **Efficacy Analysis**

The efficacy data will be descriptively summarized with the mITT and PP analysis populations and presented by study part and treatment group. Data for the Group 3 dose in both study parts will be pooled and summarized as well.

The mITT analysis will be considered primary and the PP supportive.

For all analyses of BCVA data, missing data will be imputed using multiple imputation methods. Patients who receive rescue medication/procedures within 6 months after the study treatment is initiated will be considered failure to achieve a gain of at least 15 BCVA letters. For continuous measures, all data points after a subject starts rescue medication will be replaced with the last observation prior to rescue medication administration.

Sensitivity analyses on the primary endpoint will be performed as follows:

- 1) On observed data only, with subjects requiring rescue medications prior to Month 6 included as treatment failures (mITT and PP populations)
- 2) Imputing missing data using the last observation carried forward, with subjects requiring rescue medications prior to Month 6 included as treatment failures (mITT population)
- 3) On observed data only, with subjects who require rescue medications prior to Month 6 using their Month 6 data (mITT population)

The same approach to missing data as described for BCVA data will apply to CST data.

The time to achieve a treatment response of gain of 15 or more letters from baseline BCVA will be analyzed using the Kaplan-Meier method. Survival plots will be created and the survival time will be presented as mean, median, 95% confidence intervals (CIs) for the median, and the range.

Change from baseline in number of letters read correctly (using BCVA) and change from baseline of retinal CST (by using SD-OCT scan) in the study eye during the 12-month period will be summarized by treatment groups at scheduled visits. Additionally, 95% CIs for the treatment estimates in changes from baseline will be constructed.

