### Safety Analysis

All safety data analyses will be performed on the safety population and displayed in subject data listings and summarized in tables. Treatment-emergent adverse events (TEAEs) will be listed and categorized by start date, stop date, seriousness, severity, relationship to IP, action taken, and outcome. TEAEs with a missing relationship to study treatment will assume greatest relationship to study treatment. TEAEs with missing severity grades will be categorized as "missing" for tabulation of TEAEs by severity. Summary tables will display the total number of TEAEs and the number of subjects with each TEAE by treatment groups. TEAEs will be summarized by the Medical Dictionary for Regulatory Activities (MedDRA) system organ class and preferred term for all TEAEs, serious adverse events (SAEs), and TEAEs leading to study withdrawal. In addition, TEAEs will be summarized by day of onset relative to the injection day of IP.

Safety data including physical examination, vital signs, clinical laboratory data, IOP assessments, SLB, indirect ophthalmology, FA, and FP evaluations will be descriptively summarized by treatment group.

Continuous safety data will be summarized by visit and include changes from baseline. Continuous data will also be converted to categorical values where possible (ie, below, within, and above normal ranges) and summarized in shift from baseline tables. Categorical safety data collected by visit will be summarized showing the counts and percentages in each category at each visit, as well as shifts from baseline.

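### Visual acuity loss and vitreous opacity are named product risks, but no planned summary counts measured letter loss, follows it past rescue, or gives the duration of opacity

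*Combined protocol and SAP*

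**What the plan says.** The synopsis section on known and potential risks expects "transient vitreous opacity, which might result in transient visual acuity decrease but would be expected to resolve within 2-6 weeks after study drug dosing". Its list of expected reactions is said to "include vitreous opacity, increased IOP, visual acuity decrease, conjunctival hemorrhage" and further events. Safety and tolerability by strength is a secondary objective.

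BCVA appears only among the efficacy measures. The continuous one is "Change from baseline in number of letters read correctly (using BCVA) in the study eye at scheduled visits". The categorical ones are "Proportion of subjects with BCVA gain of 15 or more letters from baseline in the study eye at scheduled visits", the same gain at 6 months as the primary endpoint, and a letter score above 73. Time to a 15-letter gain is also planned. No loss threshold is stated, and BCVA is in neither the list of safety measures nor the Safety Analysis section.

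Efficacy Analysis sets the handling: "For all analyses of BCVA data, missing data will be imputed using multiple imputation methods". For continuous measures, "all data points after a subject starts rescue medication will be replaced with the last observation prior to rescue medication administration". The sensitivity analyses on observed data apply to the primary endpoint only.

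Under Safety Analysis, TEAEs are listed with start date, stop date and outcome, and subjects are counted by preferred term and group. The one stated timing summary is this: "In addition, TEAEs will be summarized by day of onset relative to the injection day of IP". Categorical examination findings are tabulated by visit with shifts from baseline.

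**The concern.** The plan names a harm that is directly measurable in letters and gives it a time limit. It then tabulates those letters only in the direction of benefit, after imputation and replacement at rescue. Other continuous safety data are to be converted to categories and shown as shifts where possible; BCVA falls outside that rule because it is classed as efficacy.

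The question matters most in Part 2. Group 4 receives 0.84 mg in 70 µL, against 0.60 mg in 50 µL for Group 3: 0.84/0.60 = 70/50 = 1.40, or 40% more of the same formulation. It is the largest volume and drug amount of any group. Whether more subjects lose vision, or lose it for longer, bears directly on the safety objective. The planned tables would answer that only through reported adverse events and the extremes of an efficacy summary.

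**Working it through.** **1. The plan's own time limit on the visit calendar.** Inputs are the 2-6 week expectation (risk summary) and the visit schedule (synopsis), with injection on Day 1.

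- Two weeks: 1 + 14 = Day 15. Six weeks: 1 + 42 = Day 43.
- Visit windows: Day 14 ± 2 = Days 12-16; Day 30 ± 3 = Days 27-33; Day 60 ± 7 = Days 53-67.
- Day 43 lies 43 - 33 = 10 days after the Day 30 window closes and 53 - 43 = 10 days before the Day 60 window opens.

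No by-visit table can therefore show whether an opacity or a loss had resolved by week 6. AE stop dates could, but no summary of them is stated.

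**2. What the planned BCVA summary would show.** Part 2 randomizes up to 30 subjects 1:1, so up to 30/2 = 15 per group. The letter changes below are assumed, not trial data: *k* subjects lose 15 letters and 15 - *k* gain 6, so mean = (-15*k* + 6(15 - *k*))/15.

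| *k* | Mean | SD | Median | Minimum | Loss of 15 or more |
|---|---|---|---|---|---|
| 1 | 69/15 = +4.6 | 5.4 | +6 | -15 | 1/15 = 7% |
| 2 | 48/15 = +3.2 | 7.4 | +6 | -15 | 2/15 = 13% |
| 3 | 27/15 = +1.8 | 8.7 | +6 | -15 | 3/15 = 20% |

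If the other subjects gain anywhere from 5 to 10 letters, the mean for *k* = 1 to 3 runs from +1.0 to +8.3 and the minimum stays at -15. The minimum reveals that at least one subject lost 15 letters. Mean and SD move with *k*, but a reader cannot recover *k* from them without knowing the other changes. The text also does not say how a minimum is reported under multiple imputation.

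**3. What replacement at rescue does.** Take two assumed subjects. One is at -15 before rescue: -15 is carried to every later visit, whether vision recovers or not. The other is at +3 before rescue and falls to -15 afterwards: +3 is shown throughout. A loss seen before rescue is kept; persistence, recovery and new loss after rescue are not visible. One sensitivity analysis does use rescued subjects' actual Month 6 data, but only to classify a 15-letter gain.

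**4. Whether a loss count is feasible and how precise.**

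- The lowest eligible score is 19 letters, and 19 - 15 = 4, so every eligible subject can register a 15-letter loss.
- With 0 of 15, the exact upper 95% limit is 1 - 0.025^(1/15) = 22%. With 3 of 15, the exact interval is 4% to 48%.
- For Group 3 pooled over both parts, 11 + 15 = 26, and 0 of 26 gives an upper limit of 13%.
- The chance of seeing at least one such loss among 15 is 1 - (1 - *p*)^15: 54%, 79% and 96% for assumed true rates of 5%, 10% and 20%.

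**The case against.** Much of the harm is already covered. The TEAE tables count subjects with vitreous opacity or acuity decrease when reported. By-visit examination tables may count opacity if it is recorded as a finding. Listings give stop dates and outcome. With up to 15 subjects per Part 2 group, no formal comparisons and a safety monitoring committee that has reviewed unmasked listings, individual cases can be read directly. All of that stands, and it limits the weight of the point. It does not supply a count of measured loss or a duration summary in the planned tables.

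A reader might infer that BCVA is reported only as an average. It is not: SD, median, minimum and maximum are planned, as are 95% intervals for change. For *k* = 3 above, a t interval is 1.8 ± 2.145 × 8.7/√15, about -3.0 to +6.6, which is not a clear benefit.

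A reader might also infer that the mITT population leaves out losses. It cannot leave out an observed one: any treated subject with a post-treatment BCVA has an efficacy evaluation and so belongs to mITT. Nor do the documents support a claim that sites would fail to report an expected transient drop.

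The larger-dose argument has a limit too. If the stated phospholipid concentration applies to the injected volume, Group 4 carries 50 mM × 70 µL = 3.5 µmol, less than the 100 mM × 50 µL = 5.0 µmol of Group 2. Volume and drug amount are the highest given; lipid load is not.

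Finally, the supplied text is at synopsis level, so AE definitions or opacity grading may be set out elsewhere.

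**Conclusion.** The gap is real but narrow. Following the plan as supplied gives no number of subjects with a measured letter loss, no observed BCVA change after rescue, and no check of the 2-6 week expectation. In the assumed example the same median and minimum fit loss rates from 7% to 20%.

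The stronger reading, that the plan conceals harm, is not supported. Reported events are counted, the minimum exposes that a large loss occurred, and a loss recorded before rescue is carried forward rather than erased. The text gives no timing for rescue, so it cannot be said how often replacement would affect the early period in which the named risk is expected.

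The conclusion rests on the synopsis-level text being complete on these summaries and on injection falling on Day 1. This is an inexpensive improvement that bears on a stated safety objective. It is not a flaw in the primary analysis.

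**What to change.** Add two tables to Safety Analysis, by treatment group.

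1. **Measured loss.** Using observed study-eye BCVA regardless of rescue and without imputation: the number and percentage with a loss of 15 or more letters from baseline at each visit and at any visit, with the number assessed as denominator. This mirrors the trial's own gain threshold. For losses first seen by the Day 30 visit, add how many had recovered by Day 60, with recovery defined in advance (for example, no longer meeting the loss threshold) and subjects not assessed at Day 60 shown separately.
2. **Duration.** For vitreous opacity and visual-acuity-decrease TEAEs: duration from the collected start and stop dates, and the number unresolved at 6 weeks. Count the 6 weeks from dosing, as the risk summary does, and show events without a stop date as ongoing.

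The cost is a little programming; no visit, procedure or extra subject is needed. Intervals will be wide with up to 15 subjects per Part 2 group, so the tables should be read as description. With no untreated control, a loss count also cannot by itself separate a product effect from the underlying disease.
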